# **Definition of exposure**

The participants in the intervention group are defined as exposed and the participants in the control group are defined as not exposed.

**Group\_intervention** (0=control, 1=intervention)

Intake of different phytoestrogens at endpoint is based on information from the Food Frequency Questionnaire (FFQ) and the 24-h dietary recall.

**Phytoestogens\_EP\_3** (intake of phytoestrogens at endpoint divided in tertiles, calculated from the FFQ)

Lignans\_EP\_3 (intake of lignans at endpoint divided in tertiles, calculated from the FFQ)

Isoflavones\_EP\_3 (intake of isoflavones at endpoint divided in tertiles, calculated from the FFQ)

Coumestrol\_N58\_EP\_2 (dichotomized intake of coumesterol at endpoint, calculated from the FFQ)

Phyto\_24\_recall\_3 (intake of phytoestrogens at the 24-h dietary recall divided in tertiles)

The concentrations of phytoestrogens (daidzein, enterodiol, enterolactone, equol, genistein, glycetein,

Analysis plan: PRODICA, [name]
----------------------------	--------------

lariciresinol, and secoisolariciresinol) in plasma for a sub-group of participants:

**lignans\_EP\_nmol** (plasma levels of lignans at endpoint=enterolactone+ enterodiol+ lariciresinol+ seco\_EP\_nmol)

**lignans\_BL\_nmol** ((plasma levels of lignans at baseline=enterolactone+ enterodiol+ lariciresinol+ seco\_EP\_nmol)

**isoflavones\_EP\_nmol** (plasma levels of isoflavones at endpoint = daidzein\_EP\_nmol + genistein EP nmol + glycitein EP nmol + equol EP nmol)

**isoflavones\_BL\_nmol** (plasma levels of isoflavones at baseline = daidzein\_EP\_nmol + genistein\_EP\_nmol + glycitein\_EP\_nmol + equol\_EP\_nmol)

**phytoestrogens\_EP\_nmol** (plasma levels of total phytoestrogens at baseline = enterolactone\_EP\_nmol + enterodiol\_EP\_nmol + lariciresinol\_EP\_nmol + seco\_EP\_nmol + daidzein\_EP\_nmol + genistein\_EP\_nmol + glycitein\_EP\_nmol + equol\_EP\_nmol)

phytoestrogens\_BL\_nmol (plasma levels of total phytoestrogens at endpoint =
enterolactone\_BL\_nmol + enterodiol\_BL\_nmol + lariciresinol\_BL\_nmol + seco\_BL\_nmol +
daidzein\_BL\_nmol + genistein\_BL\_nmol + glycitein\_BL\_nmol + equol\_BL\_nmol)

lignans\_diff\_nmol = lignans\_EP\_nmol - lignans\_BL\_nmol

isoflav\_diff\_nmol= isoflavones\_EP\_nmol - isoflavones\_BL\_nmol

phyto\_diff\_nmol= phytoestrogens\_EP\_nmol - phytoestrogens\_BL\_nmol

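### Baseline plasma isoflavones are defined from endpoint terms, so their change is 0 as written; the baseline lignan sum has a related slip

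*SAP*

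**What the plan says.** The section Definition of exposure lists six summed plasma variables and three changes, for a sub-group of participants.

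- **Isoflavones.** The endpoint variable sums the endpoint values of daidzein, genistein, glycitein and equol. The baseline variable is given as "plasma levels of isoflavones at baseline = daidzein\_EP\_nmol + genistein\_EP\_nmol + glycitein\_EP\_nmol + equol\_EP\_nmol". The change is "isoflav\_diff\_nmol= isoflavones\_EP\_nmol - isoflavones\_BL\_nmol".
- **Lignans.** The endpoint line reads "plasma levels of lignans at endpoint=enterolactone+ enterodiol+ lariciresinol+ seco\_EP\_nmol" and the baseline line reads "plasma levels of lignans at baseline=enterolactone+ enterodiol+ lariciresinol+ seco\_EP\_nmol". The change is "lignans\_diff\_nmol = lignans\_EP\_nmol - lignans\_BL\_nmol".
- **Total phytoestrogens.** The sum named `phytoestrogens_EP_nmol` uses eight endpoint terms but is described as "plasma levels of total phytoestrogens at baseline = enterolactone\_EP\_nmol" and so on. Its counterpart is introduced as "phytoestrogens\_BL\_nmol (plasma levels of total phytoestrogens at endpoint" but sums eight baseline terms, among them "daidzein\_BL\_nmol + genistein\_BL\_nmol + glycitein\_BL\_nmol + equol\_BL\_nmol".

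Under Additional analysis, the SAP sets out to study the effect of the diet on plasma phytoestrogens. It names Cohen's kappa between intake tertiles and plasma tertiles, boxplots, and linear regressions of plasma on estimated intake, stratified by arm and genotype.

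**The concern.** These lines are working definitions that a programmer may copy as they stand. The baseline isoflavone variable would then hold endpoint values under a baseline name, and the isoflavone change would carry no information. The lignan change would be empty or incomplete.

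The section also contradicts itself. The total consists of exactly the four lignans and the four isoflavones, so the total change should equal the lignan change plus the isoflavone change. As printed, it does not.

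**Working it through.** There is no sample size or power figure to reproduce. The check substitutes the printed definitions into the three change formulas, with no data and no assumed values.

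**Step 1, visit suffixes in the three baseline lines**

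| Baseline variable | Endpoint terms | Baseline terms | No suffix |
|---|---|---|---|
| `isoflavones_BL_nmol` | 4 | 0 | 0 |
| `lignans_BL_nmol` | 1 | 0 | 3 |
| `phytoestrogens_BL_nmol` | 0 | 8 | 0 |

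**Step 2, isoflavone change.** Write D, G, Y and Q for daidzein, genistein, glycitein and equol.

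`isoflav_diff_nmol` = (D_EP + G_EP + Y_EP + Q_EP) − (D_EP + G_EP + Y_EP + Q_EP) = 0.

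All four terms cancel, whatever the data.

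**Step 3, lignan change.** The right-hand sides of the two lines are identical. Three readings are possible.

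- *Literal:* identical sums are subtracted, so the change is 0.
- *The final suffix covers the whole sum:* the endpoint line is then right, and the baseline line repeats the isoflavone error. The change is again 0.
- *Terms without a suffix take the visit of their own line:* the enterolactone, enterodiol and lariciresinol changes remain, and seco_EP − seco_EP = 0. Three of four component changes survive, and the secoisolariciresinol change is lost.

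**Step 4, total change.** `phyto_diff_nmol` subtracts eight baseline terms from eight endpoint terms, which leaves eight complete component changes. The swapped descriptions do not alter this, because the variable names and the summed terms agree with each other.

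**Step 5, consistency.** With correct baseline sums, lignan change + isoflavone change = 4 + 4 = 8 component changes, which equals the total. As printed, the two parts contain 0 + 0 = 0 of the 8, or 3 + 0 = 3 of the 8 on the most lenient reading. The parts thus miss 8 or 5 of the component changes that the total includes.

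**Step 6, intent.** The baseline total already lists the four isoflavone terms that the baseline isoflavone line should use. The dietary intake sums under Variables to analyze also build their baseline isoflavones and lignans from baseline terms. The intended definition is not in doubt.

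**The case against.** The strongest reply is that this is a copying slip without consequence. The variable name, the description as baseline and the correct total line all reveal the intent. No listed analysis names any of the three plasma change variables. The SAP refers to an attached variable list for detail on created variables, and that list, which was not available for this check, may hold the right formulas. All of this stands, and it limits the weight of the point. It does not remove it: the printed definition gives a wrong value, and a correct appendix would still disagree with the main text.

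A reader might infer that the plasma results as a whole, or even the main results, are compromised. The SAP does not support that. The total change is valid, and Ki-67, PSA and the hormones do not depend on these variables.

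A reader might also infer that the SAP plans no comparison of plasma between arms. That is too strong. Kappa, the boxplots and the regressions within each arm do not estimate a difference between arms, and the section Receptor expression shows that the SAP can state such a comparison outright. However, the t-test or Mann-Whitney test under Statistical models applies to variables listed further down. The nearest list holds covariates only, but the plasma analysis also comes later and may be meant. One part of the text after Receptor expression was not available either, so absence cannot be claimed firmly.

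**Conclusion.** The definitions are wrong as written, and the severity is minor. The isoflavone change is 0 for every man with plasma data; this is algebra and needs no assumption. The lignan change is 0, or keeps three of its four components, depending on how the terms without a suffix are read. The total change is right on all eight components, with its two descriptions swapped. These statements concern the SAP text; whether the analysis code carries the error depends on the variable list.

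The practical effect is confined to a sub-group and an additional analysis. It becomes real only if the isoflavone or lignan baseline or change variables are used.

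The lack of a clearly stated arm comparison for plasma is a request for clarification, held with lower confidence, and not a second error.

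**What to change.** 1. Define `isoflavones_BL_nmol` and `lignans_BL_nmol` from baseline concentrations only.
2. Give every lignan term its visit suffix in both lignan lines.
3. Swap the descriptions of the two total phytoestrogen sums.
4. Check the attached variable list, and any code already written from it, for the same slips. A simple test is that the isoflavone and lignan changes add up to the total change for each man.
5. Optional: say whether the group test under Statistical models applies to plasma. Alternatively, name a regression of endpoint concentration on arm, adjusted for the corrected baseline. The correction must come first: with the printed isoflavone formula the covariate equals the outcome, so the fit is exact with slope 1 on the covariate and 0 on arm.

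The cost is a short text correction, one check of the variable list and, if wanted, one added sentence. No new data are needed.

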### Definition of effect modifying factor

The individual genotype (alleles TT, TC or CC) of the estrogen-beta-gene (ERB) are identified in the blood sample at baseline.

**cat\_genotype** (created from variable Genotype, 0=TT, 1= TT/CC)

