### PLANS FOR STATISTICAL ANALYZES

### VARIABLES TO ANALYZE

Created variables (for more details see attached variable list):

BMI (kg/m^2): BMI\_stata = Weight\_inclusion / ((Lenght\_inclusion/100) \* (Lenght\_inclusion/100) BMI\_group = 1= under weight (BMI <18.5); 2= normal weight (BMI 18.5-24.9); 3= Overweight (BMI 25-29.9); 4= Obese class (BMI 30-34.9) 1; 5= Obese class ≥2 (BMI ≥35)

Weight change (kg): Weight\_diff = Weight\_endpoint - Weight\_inclusion

Analysis plan: PRODICA, [name]	Version 2
---------------------------------------	-----------

Compliance (1= compliance >80; 0= compliance <80 %): Compliance 24 recall (based on reported intake of phytoestrogens at the 24-h dietary recall) Compliance intervention 24 r (based on eaten interventions foods reported from at the 24-h dietary recall) Compliance intervention (based on eaten interventions foods reported from at the end of the intervention) Intake of isoflavones (µg): Isoflavones BL = Genistein N56 BL + Daidzein N57 BL + Formononetin N59 BL + Biochanin N60 BL + Equol N75 BL Isoflavones EP = GenisteinN56 EP + Daidzein N57 EP + Formononetin N59 EP + Biochanin N60 EP + Equol N75 EP. Intake of lignans (µg): Lignans BL = SECOtot N61 BL + Matairesinol N62 BL Lariciresinol N71 BL + Pinoresinol N72 BL + Syringaresinol N73 BL + Medioresinol N74 BL + Enterodiol N76 BL + Enterolactone N77 BL Lignans EP=SECOtot N61 EP + Matairesinol N62 EP + Lariciresinol N71 EP + Pinoresinol N72 EP + Syringaresinol N73 EP + Medioresinol N74 EP + Enterodiol N76 EP + Enterolactone N77 EP Intake of phytoestrogens (ug): Phytoestogens BL = (Isoflavones BL + Lignans BL + Coumestrol N58 BL) Phytoestogens EP =(Isoflavones EP + Lignans EP + Coursetrol N58 EP) Level of physical activity: Physical activity BL group = low, moderate or high 1 = Low physical activity (101, 102, 103 or 201 points) 2 = Moderate physical activity (104, 202, 203, 301 or 302 points) 3 = High physical activity (204, 303, 304, 401, 402, 403 or 404 points) Intake of fatty fish: Fat fish group BL:  $0 \le 1$  times/month; 1 = 1-3 times/month;  $2 \ge 1$  times/week Fat fish group EP: 0 = <1 times/month; 1 = 1-3 times/month; 2 = >1 times/week Fat fish diff: Fat fish month EP - Fat fish month BL

Use of antibiotics:

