### Stratification by ERß alleles and test of interaction:

Analysis of hypothesis above (C0- C07 and corresponding models) will be stratified by genotype of

Analysis plan: PRODICA, [name]
---------------------------------------

ERβ (variable: cat\_genotype).

Interactions between exposure and ERß SNPs on the outcome will be evaluated on the additive effect scales. Effects will be measured by RDs and interaction will be assessed in a generalized linear model by the product term between the covariates representing phytoestrogen intake and SNP genotypes.

Product term: int1=intervention\*cat\_genotype

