### Additional analysis:

Intention-to-treat-analyses: All participants will be included.

*Per-protocol-analyzes*: All participants with  $\geq 80$  % compliance will be included.

In the intervention group, compliance will be considered as  $\geq 80$  percent of the recommended intake of 200 mg of phytoestrogens, which is equal to  $\geq 160$  mg. In the control group, intakes below 160 mg of phytoestrogens will be considered compliant.

Analysis of hypothesis will be stratified for:

- no use of antibiotics vs. use of antibiotics
- no use of finasteride vs. use of finasteride

Investigate the effects of the intervention diet on plasma concentrations of phytoestrogens: Cohen's Kappa will be used to compare the agreement of classifications in tertiles from estimated intake of phytoestrogens and plasma concentrations of phytoestrogens. (Kappa values <0 will be considered as poor, 0.00-0.20 as slight, 0.21-0.40 as fair, 0.41-0.60 as moderate, 0.61-0.80 as substantial, and 0.81-1.00 as almost perfect). Boxplots will be used to present the data graphically. Linear regressions will be used to investigate the relationships between estimated intake concentrations (explanatory variables) and plasma concentrations of phytoestrogens (outcomes). The regression model will be stratified according to the intervention- and control groups and genotype.

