#### Receptor expression

The mRNA levels of ER $\alpha$ , ER $\beta$ , and AR will be compared between intervention- and control groups and groups of genotype.

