## APPENDICES

Appendics 1 - Variable list

Appendics 2 - Food Frequency Questionnaire

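### The genotype variable cat_genotype is coded so that TT falls under both values and TC under neither; it needs correcting before the genotype strata and the interaction term are built

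*SAP*

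**What the plan says.** In the SAP, *Definition of effect modifying factor* states: "The individual genotype (alleles TT, TC or CC) of the estrogen-beta-gene (ERB) are identified in the blood sample at baseline". The next line defines the analysis variable cat_genotype as "created from variable Genotype, 0=TT, 1= TT/CC".

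*Stratification by ERß alleles and test of interaction* puts this variable to use. It says "Analysis of hypothesis above (C0- C07 and corresponding models) will be stratified by genotype of" ERβ and names cat_genotype as the variable. It then defines the interaction by "Product term: int1=intervention" multiplied by cat_genotype.

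Two further places group by genotype without naming a variable or codes. For the plasma analyses in *Additional analysis*: "The regression model will be stratified according to the intervention- and control groups and genotype". For the mRNA levels in *Receptor expression*: "will be compared between intervention- and control groups and groups of genotype".

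*Variables to analyze* refers the reader to an appendix on created variables ("for more details see attached variable list"), and the appendix is listed as "Appendics 1 - Variable list". Its content is not shown.

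**The concern.** A binary grouping of three genotypes must give each genotype exactly one code. The printed line does not: its two codes overlap on TT and leave TC out.

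The second of the SAP's two hypotheses is that any effect of phytoestrogens on tumor proliferation is modified by this SNP. cat_genotype is the only variable defined under the heading on effect modification, and both the strata and int1 depend on it. An analyst who follows the line must either guess the intention or run code whose result depends on the order of its statements. If no other document fixes the coding, the grouping could also be settled after results have been seen.

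**Working it through.** No sample size, power or error rate is involved, so the check is one of set membership followed by a count of the analyses affected.

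**1. Codes per genotype as printed** (*Definition of effect modifying factor*)

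| Genotype | Under code 0 (TT) | Under code 1 (TT/CC) | Number of codes |
|---|---|---|---|
| TT | yes | yes | 2 |
| TC | no | no | 0 |
| CC | no | yes | 1 |

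Only 1 of 3 genotypes has exactly one code.

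**2. What literal programming would produce**

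- Code 0 assigned first, code 1 second: TT and CC both end as 1, nobody is 0 and TC is missing. One stratum remains, and int1 = intervention × 1 = intervention, so no interaction can be estimated.
- Code 1 assigned first, code 0 second: TT = 0, CC = 1 and TC is missing. All heterozygotes drop out and the contrast is TT against CC.

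**3. Which repairs are valid**

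Keep 0=TT. The possible pairs for code 1 are TT/TC, TT/CC and TC/CC, and only TC/CC covers all three genotypes once each.

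If code 0 is not taken as correct, consider each of the six single-letter changes to the printed TT, TT/CC, reading CT as TC. Four give a valid grouping, and they amount to two distinct codings:

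- 0=TT, 1=TC/CC (TT homozygotes against C carriers);
- 0=TC, 1=TT/CC (heterozygotes against homozygotes).

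The first keeps the printed reference group and is the more natural reading. The second cannot be excluded from the text shown.

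**4. How many analyses use the variable** (crude models in *Statistical models*)

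- Outcomes: Ki-67 (counted once), PSA_total_diff, PSA_ratio_diff, estradiol_diff_cat, testo_diff_cat, testo_estrad_ratio_diff, testo_SHBG_ratio_diff = 7.
- Exposures: intervention group, phytoestrogens, isoflavones, lignans, coumestrol = 5.
- Crude models: 7 × 5 = 35. Stratum-specific fits: 35 × 2 = 70, plus int1.
- Part concerning tumor proliferation, the outcome named in hypothesis 2: Ki-67 only, so 1 × 5 = 5 crude models and 5 × 2 = 10 stratum fits, plus int1 for that outcome.

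**The case against.** The strongest reply is that this is a slip of one letter. The sentence directly above lists TT, TC and CC, most readers would take code 1 as TC/CC, and no result changes once the line is put right. The raw Genotype variable keeps all three categories, so no information is lost. The variable list may already hold the correct coding, and since it is not shown it cannot be called missing. Hypothesis 2 concerns tumor proliferation alone, so most of the 70 fits do not bear on it. Finally, a misread letter when the PDF was converted is possible.

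Much of this stands. The error is probably typographical. The count of 70 measures how widely the variable is used, not how far any estimate would move. The hypothesis-2 share is 10 stratum fits plus int1. The risk of a grouping chosen after the fact exists only if the appendix does not fix the coding. A conversion error cannot be ruled out, although nothing in that section points to one.

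It does not remove the point. The line is the operative definition of the effect modifier, no other text shown gives a coding, and two valid repairs lie one letter away. If the appendix is right, the SAP text contradicts it and still needs correction.

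**Conclusion.** The concern holds. As written, cat_genotype is not a valid grouping: 2 of 3 genotypes (TT and TC) lack a unique code, and neither the strata nor int1 can be built as intended without a choice that the text shown does not make. The reach is 70 stratum-specific fits and the interaction term; the 35 unstratified crude models, including the comparison of randomized groups, are unaffected. Hypothesis 2 is also conditional on an effect existing. The point should be fixed, but it does not threaten the primary comparison.

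The count takes Ki-67 as one outcome and covers only the crude models listed. No allele frequency is assumed. That 1=TC/CC was intended is an inference, though the most plausible one.

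**What to change.** Before any genotype analysis, including any done at the interim look if genotype is part of it:

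- Correct the definition so that each genotype has exactly one code, most plausibly 0=TT, 1=TC/CC. The sponsor should confirm the intended grouping and bring the SAP text and the Appendix 1 variable list into agreement.
- Use that coding for the strata and for int1.
- State whether the genotype groups in the plasma regressions and in the receptor comparison use the same coding or all three genotypes.

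The cost is a one-line SAP correction, a short clarification in two sections and a check of the variable list.

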### PLANS FOR STATISTICAL ANALYZES

### VARIABLES TO ANALYZE

Created variables (for more details see attached variable list):

BMI (kg/m^2): BMI\_stata = Weight\_inclusion / ((Lenght\_inclusion/100) \* (Lenght\_inclusion/100) BMI\_group = 1= under weight (BMI <18.5); 2= normal weight (BMI 18.5-24.9); 3= Overweight (BMI 25-29.9); 4= Obese class (BMI 30-34.9) 1; 5= Obese class ≥2 (BMI ≥35)

Weight change (kg): Weight\_diff = Weight\_endpoint - Weight\_inclusion

Analysis plan: PRODICA, [name]	Version 2
---------------------------------------	-----------

Compliance (1= compliance >80; 0= compliance <80 %): Compliance 24 recall (based on reported intake of phytoestrogens at the 24-h dietary recall) Compliance intervention 24 r (based on eaten interventions foods reported from at the 24-h dietary recall) Compliance intervention (based on eaten interventions foods reported from at the end of the intervention) Intake of isoflavones (µg): Isoflavones BL = Genistein N56 BL + Daidzein N57 BL + Formononetin N59 BL + Biochanin N60 BL + Equol N75 BL Isoflavones EP = GenisteinN56 EP + Daidzein N57 EP + Formononetin N59 EP + Biochanin N60 EP + Equol N75 EP. Intake of lignans (µg): Lignans BL = SECOtot N61 BL + Matairesinol N62 BL Lariciresinol N71 BL + Pinoresinol N72 BL + Syringaresinol N73 BL + Medioresinol N74 BL + Enterodiol N76 BL + Enterolactone N77 BL Lignans EP=SECOtot N61 EP + Matairesinol N62 EP + Lariciresinol N71 EP + Pinoresinol N72 EP + Syringaresinol N73 EP + Medioresinol N74 EP + Enterodiol N76 EP + Enterolactone N77 EP Intake of phytoestrogens (ug): Phytoestogens BL = (Isoflavones BL + Lignans BL + Coumestrol N58 BL) Phytoestogens EP =(Isoflavones EP + Lignans EP + Coursetrol N58 EP) Level of physical activity: Physical activity BL group = low, moderate or high 1 = Low physical activity (101, 102, 103 or 201 points) 2 = Moderate physical activity (104, 202, 203, 301 or 302 points) 3 = High physical activity (204, 303, 304, 401, 402, 403 or 404 points) Intake of fatty fish: Fat fish group BL:  $0 \le 1$  times/month; 1 = 1-3 times/month;  $2 \ge 1$  times/week Fat fish group EP: 0 = <1 times/month; 1 = 1-3 times/month; 2 = >1 times/week Fat fish diff: Fat fish month EP - Fat fish month BL

Use of antibiotics:

antiobotics\_1y\_dic (0= no intake last year or don't know;  $1=\ge 1$  time last year) antiobotics\_2\_5y\_dic (0= no intake last 2-5 years or don't know;  $1=\ge 1$  time last 2-5 years) f53\_1\_EP: Intake of antibiotics in recent weeks at endpoint (0= No; 1=Yes) antibiotics\_all (0= no intake during intervention and last 5 years or don't know;  $1=\ge 1$  time during intervention and last 5 years)

Smoking:

- 0= never smoked or quitted smoking >5 years ago
- 1= Current smoker or quitted smoking  $\leq$ 5 years ago

